6.2 SAFETY ENDPOINTS

Incidence and severity of all adverse events including serious adverse events (SAEs). The reporting of safety data will be in accordance with Pfizer Data Standards.

Variable	Role	Data source(s)	Operational definition
Occurrence of adverse events	Safety outcome	Case records	Number and percentage of SOC and PT according to maximal grade of adverse event (patient based)
Occurrence of adverse drug reactions	Safety outcome	Case records	Number and percentage of SOC and PT according to maximal grade of adverse drug reaction (patient based)
Occurrence of serious adverse events	Safety outcome	Case records	Number and percentage of SOC and PT according to maximal grade of serious adverse event (patient based)
Occurrence of serious adverse drug reactions Safety outcome		Case records	Number and percentage of SOC and PT according to maximal grade of serious adverse drug reaction (patient based)
Reason for seriousness	Safety outcome	Case records	Number and percentage for each reason (event based)
Occurrence of scenarios involving drug exposure Safety outcome		Case records	Number and percentage (patient based)
Reason for scenario involving drug exposure	Safety outcome	Case records	Number and percentage for each reason (event based)
Worst outcome	Safety outcome	Case records	Number and percentage (patient based), order: recovered,

			recovered with sequelae, not recovered, unknown, fatal
Action taken	Safety outcome	Case records	Number and percentage for each reason (event based)
Type and results of performed laboratory checks	Potential confounder, potential subgroup identifier, safety outcome	Case records	Summary statistics (n, mean, median, standard deviation, minimum and maximum) of the minimal and maximal value per patient, respectively

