5.2 SAFETY ANALYSIS SET

The Safety Analysis Set (SAF) consists of all patients with informed consent who received at least one dose of abrocitinib.

This population will be used for safety analysis, i.e. for the analysis of adverse events and laboratory values.

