5.3 OTHER ANALYSIS SET

The modified Full Analysis Set (mFAS) consists of all patients who met the eligibility criteria, received at least one dose of abrocitinib and had at least one post-baseline visit. This population will be used for analysis of primary and secondary endpoints, if $\geq 10\%$ of the FAS is omitted.

The Per Protocol Set (PP) consists of all patients who met the eligibility criteria, received at least one dose of abrocitinib and completed all visits, irrespective of the time-window.

This population will be used for analysis of primary and secondary endpoints, if $\geq 10\%$ of the mFAS is omitted.

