8.2.1 Safety Analyses

Treatment-emergent adverse events are adverse events which worsen or start after start of treatment with abrocitinib but no later than 28 days after end of treatment with abrocitinib.

In addition to the analysis of treatment-emergent adverse events and drug-related adverse events as specified in 6.2 adverse events which occurred under another systemic treatment, following cessation of abrocitinib, will be given and presented in a separated listing. Number and percentage of SOC and PT will be presented according to maximal grade.

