Outcome **Analysis Set Supports Missing Data** Subgroups Statistical Method Covariates/ Strata Protocol **Objective** Number baseline)/score at baseline*100 Mann-Whitney-U test for subgroups Change of EuroQol five-(score at respective FAS, mFAS, PP All None Excluded dimensional-five level visit - score at (EQ-5D-5L) from baseline)/score at 21 baseline baseline*100 Mann-Whitney-U test for subgroups Change of PBI from FAS, mFAS, PP All (score at respective None Excluded visit - score at baseline baseline)/score at 22 baseline*100 Mann-Whitney-U test for subgroups Patient's satisfaction FAS, mFAS, PP All Frequency tables for None Excluded satisfaction with with treatment (PBI after baseline) effectiveness and tolerability 23 Chi-Square test respective Fisher's exact test for subgroups Number of days with FAS, mFAS, PP All Excluded Summary statistics (n, None topical-treatment use mean, median, standard deviation, (TCS, TCI) 24 minimum and maximum) Mann-Whitney-U test for subgroups Number of days with FAS, mFAS, PP All Summary statistics (n, None Excluded emollients use mean, median, standard deviation, 25 minimum and maximum)

Outcome	Analysis Set	Supports Protocol Objective Number	Subgroups	Statistical Method	Covariates/ Strata	Missing Data
				Mann-Whitney-U test for subgroups		
AD-treatment with abrocitinib and/or without topicals – total days	FAS, mFAS, PP	26	All	Summary statistics (n, mean, median, standard deviation, minimum and maximum) Mann-Whitney-U test for subgroups	None	Excluded
AD-treatment with abrocitinib and/or without topicals – stratified by abrocitinib dose	FAS, mFAS, PP	27	All	Summary statistics (n, mean, median, standard deviation, minimum and maximum) Mann-Whitney-U test for subgroups	None	Excluded
Number of flares	FAS, mFAS, PP	28	All	Summary statistics (n, mean, median, standard deviation, minimum and maximum) Mann-Whitney-U test for subgroups	None	Excluded

All explorative endpoints mentioned in section 6.3 will be analyzed for FAS and all subgroups, respectively. Safety enpoints, as given in section 6.2 will be analyzed for SAF.

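### SAP 6.2 gives adverse-event incidence only as a crude percentage of all dosed patients, without time at risk, so it tends to understate 12-month on-treatment risk

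*SAP*

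**What the plan says.** - **Measure.** SAP 6.2 introduces the endpoint as "Incidence and severity of all adverse events including serious adverse events (SAEs" and defines it operationally as "Number and percentage of SOC and PT according to maximal grade of adverse event (patient based". The rows for adverse drug reactions (ADRs), SAEs and serious ADRs have the same form. None uses person-time.
- **Denominator.** SAP 5.2: "The Safety Analysis Set (SAF) consists of all patients with informed consent who received at least one dose of abrocitinib". SAP 8.2.3: "Safety enpoints, as given in section 6.2 will be analyzed for SAF". No contact after baseline is required.
- **Counting window.** SAP 8.2.1 treats an event as treatment-emergent if it starts or worsens after the start of abrocitinib but "no later than 28 days after end of treatment with abrocitinib". Events under a later systemic treatment go to a separate listing.
- **Follow-up.** SAP 1.1 makes no visit mandatory. Observation is planned for 12 months and continues after a switch of therapy. SAP 7 generally does not impute missing data.
- **Effectiveness, for contrast.** SAP 5.3 defines an mFAS of patients who, among other conditions, "had at least one post-baseline visit". Its use is conditional and confined to effectiveness: "This population will be used for analysis of primary and secondary endpoints, if" at least 10% of the FAS drops out. Safety has no counterpart.
- **Exposure and time to event.** SAP 6.3 derives total treatment days but does not connect them with AEs. Protocol 9.7 names Kaplan-Meier for time-to-event endpoints in general; neither document names an AE endpoint of that kind.

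**The concern.** A patient-based percentage equals a risk over a stated period only if everyone in the denominator was observed for that period. Two groups here were not.

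The first is patients dosed at baseline and never documented again. They remain in the SAF and will usually show no event because nobody recorded one. The second is patients who stop early. One who stops at week 6 has about 10 weeks (6 weeks plus 28 days) in which a treatment-emergent event can count, yet weighs as much as a patient treated for 12 months.

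The percentage therefore mixes risk with length of observation. Safety is one of the explorative objectives, and a reader of the final report is likely to take a figure called incidence, from a study with 12 months of observation, as the 12-month risk on abrocitinib. Read that way, it tends to be too low. It would also fall with poorer follow-up or shorter persistence even if the underlying risk were unchanged, which hampers comparison with other sources.

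**Working it through.** The documents state no AE rate, loss rate or discontinuation rate, and there is no sample-size calculation, so there is no plan figure to reproduce. What follows is an illustration.

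**Inputs from the documents:** 12 months of observation (SAP 1.1); a 28-day tail after the last dose (SAP 8.2.1); all dosed patients in the denominator (SAP 5.2); at least 750 patients planned (SAP 1.2).

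**Assumptions:**
- p, the 12-month risk under full exposure: 2% to 60%
- u, the share never seen after baseline: 5% or 10%
- s, the share stopping at a time uniform over the year: 20% or 30%
- a constant hazard, and stopping unrelated to AEs

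**Formulas**, with time in months and c = 28/30.4375 = 0.92:
- hazard: λ = −ln(1 − p)/12
- average risk among stoppers, at risk until the earlier of stop + c and 12 months: a = 1 − (1/12)·[(e^(−λc) − e^(−12λ))/λ + c·e^(−12λ)]
- expected crude percentage: s·a + (1 − u − s)·p

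**Worked case, p = 10%:** λ = 0.00878 and a = 5.82%.
- u = 5%, s = 20%: 0.20 × 5.82% + 0.75 × 10% = 8.7%, about 65 patients of 750 instead of 75.
- u = 10%, s = 30%: 0.30 × 5.82% + 0.60 × 10% = 7.7%, about 58 of 750.

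**Ratio of the crude percentage to p:**

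| p | u = 5%, s = 20% | u = 10%, s = 30% |
|---|---|---|
| 2% | 0.865 | 0.773 |
| 10% | 0.866 | 0.775 |
| 30% | 0.871 | 0.781 |
| 60% | 0.880 | 0.794 |

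The ratios run from 0.773 to 0.880, a relative shortfall of about 12% to 23%.

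**Split between the two sources.** Take a first-event rate of 0.6 per year, so that p = 1 − e^(−0.6) = 45.1%. With u = 10% and s = 30% the crude figure is 35.5%, a shortfall of 9.6 points. Unseen patients account for 0.10 × 45.1 = 4.5 points and early stopping for the other 5.1. With u = 5% and s = 20% the crude figure is 39.5%.

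**Sensitivity to timing.** If all events fall in the first 30 days, the 28-day tail captures almost everything and stoppers lose practically nothing (ratio 0.9998). The unseen share still lowers the percentage by exactly u, whatever the timing.

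**Scale.** At 750 patients the 95% half-width for 30% is 1.96 × √(0.3 × 0.7/750) = 3.3 points. For p = 30%, u = 10%, s = 30% the expected figure is 23.4%, a shortfall of 6.6 points, so the effect can exceed sampling error.

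**The case against.** The strongest reply is that the share of dosed patients with a recorded AE is a legitimate description, and that a single-arm study with no hypotheses promises no more. It is low only against a different target, the 12-month risk under continued treatment, which the SAP does not claim to estimate. This stands, and is why the SAF percentages should stay. It does not help the reader who needs to know how much observation lies behind them.

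Three stronger readings are tempting, and the documents do not support them:

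- *Early stoppers count as event-free.* They do not. Any event from first dose to 28 days after the last counts, including one that caused the stop. All AEs in the reporting period are to be analysed (SAP 1.1), and switchers stay under observation. Only the shortness of their time at risk is ignored, and only for treatment-emergent counts.
- *The SAP expects 10% or more of patients to have no post-baseline visit.* SAP 5.3 sets a trigger for using the mFAS; it is not a forecast.
- *The schedule prevents early events from being recorded.* The AE row has no entry at baseline, but Protocol 11 starts safety reporting at informed consent and requires all non-serious AEs on the eCRF. What matters is absence of later contact, not the layout of the table.

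Two further cautions stand. Intolerability is a documented reason for stopping, so independence of stopping and AEs is doubtful. SAP 6.2 also refers to sponsor data standards and SAP 9 to separate table mock-ups; neither is available here, so an exposure-adjusted table may exist there. The SAP, where the endpoint is defined, specifies none.

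**Conclusion.** The point holds in a limited form. SAP 6.2 reports AE incidence only as a crude percentage of the SAF, nothing in either document links AEs to time at risk, and patients without post-baseline contact are not counted or shown for safety. Read as 12-month on-treatment risk, the figure tends to be too low.

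The size cannot be fixed from the documents. The relative shortfall of about 12-23% rests wholly on the assumed 5-10% unseen, 20-30% stopping evenly, a constant hazard and stopping unrelated to AEs. With front-loaded events only the unseen share remains. A reader might infer that the planned percentages are wrong and must be replaced. They are not: they describe recorded events correctly and need a companion figure. This is a cheap improvement.

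**What to change.** 1. Leave the SAF percentages in SAP 6.2 unchanged.
2. In SAP 6.2 and 8.2.1 add, at least for any AE, SAE, ADR and serious ADR, and by SOC/PT where counts allow, the number of patients with a first treatment-emergent event per 100 patient-years. Count time from first dose to the earliest of first event, 28 days after last dose, or last contact.
3. Report the number of SAF patients with no post-baseline contact beside the AE tables.
4. If a sensitivity percentage without these patients is wanted, define exclusion by contact alone. Keeping uncontacted patients only when an event was reported would select on the outcome and push the percentage up.
5. State next to the rate that it is readily interpretable only if the hazard is roughly constant. For front-loaded events it can mislead.

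Cost: SAP wording and one extra column, from treatment and visit dates already collected. If the sponsor standards or mock-ups already contain such a table, a cross-reference in SAP 6.2 is enough.

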6.3 OTHER ENDPOINTS

Variable	Role	Data source(s)	Operational definition	
AD-treatment with abrocitinib and/or without topicals – total days	Exposure, Potential confounder, potential subgroup identifier	Case records	Date of last treatment – date of first treatment +1 Summary statistics (n, mean, median, standard deviation, minimum and maximum)	
AD-treatment with abrocitinib and/or without topicals – stratified by abrocitinib dose Exposure, Potential confounder, outcome, potential subgroup identifier		Case records	Date of last treatment – date of first treatment +1 Summary statistics (n, mean, median, standard deviation, minimum and maximum) stratified by the abrocitinib dose most often applied during the study	
Age (Year of birth)	Baseline characteristics, potential confounder, potential subgroup identifier	Case records	Age=year of IC – year of birth Summary statistics (n, mean, median, standard deviation, minimum and maximum)	
Sex	Baseline characteristics, potential confounder, potential subgroup identifier	Case records	Frequency analysis	
Height Baseline characteristics		Case records	Summary statistics (n, mean, median, standard deviation, minimum and maximum)	
Weight Baseline characteristics		Case records	Summary statistics (n, mean, median, standard deviation, minimum and maximum)	
Highest level of education	Baseline characteristics, potential confounder	Case records	Frequency analysis	
Ethnicity Baseline characteristics		Case records	Frequency analysis	

Occupational status	Baseline characteristics	Case records	Frequency analysis
Alcohol consumption status	Baseline characteristics, potential confounder	Case records	Frequency analysis
Insurance type	Baseline characteristics	Case records	Frequency analysis
Presence of family history of atopic diseases	Baseline characteristics, potential confounder, potential subgroup identifier	Case records	Frequency analysis
History of herpes simplex and/or eczema herpeticum and/or herpes zoster	Baseline characteristics	Case records	Frequency analysis
Vaccination status (Herpes zoster, Covid-19, Influenza Varicella)	Baseline characteristics	Case records	Frequency analysis
Age at initial diagnosis of AD	Baseline characteristics, potential confounder	Case records	Age at initial diagnosis =year of initial diagnosis – year of birth 1. Summary statistics (n, mean, median, standard deviation, minimum and maximum) 2. Categorical: < 12 y, 12-<18 y and ≥ 18 y
Smoking history and current smoking status	Baseline characteristics, potential confounder	Case records	Frequency analysis
Renal and/or liver impairment	Baseline characteristics	Case records	Frequency analysis
Comorbidities at baseline	Baseline characteristics, potential confounder, potential subgroup identifier	Case records	Frequency analysis
If positive anamnesis at baseline exists: Improvement of (allergic) asthma symptoms from baseline	Baseline characteristics, potential confounder, potential subgroup identifier	Case records	Frequency analysis
If positive anamnesis at baseline exists: Improvement of (allergic) rhinitis symptoms from baseline	Baseline characteristics, potential confounder, potential subgroup identifier	Case records	Frequency analysis
If positive anamnesis at baseline exists: Improvement of polyposis nasi symptoms from baseline	Baseline characteristics, potential confounder, potential subgroup identifier	Case records	Frequency analysis
If positive anamnesis at baseline exists: Improvement of alopecia areata from baseline Baseline characteristics, potential confounder, potential subgroup identifier		Case records	Frequency analysis

If positive anamnesis at baseline exists: Improvement of chronic hand eczema symptoms from baseline	Baseline characteristics, potential confounder, potential subgroup identifier	Case records	Frequency analysis
If positive anamnesis at baseline exists: Improvement of prurigo nodularis symptoms from baseline	Baseline characteristics, potential confounder, potential subgroup identifier	Case records	Frequency analysis
Previous treatments for diagnosed AD	Baseline characteristics, potential confounder, potential subgroup identifier	Case records	Frequency analysis
Concomitant treatment of AD (and dosage)	Baseline characteristics, Exposure, explorative outcome, potential confounder, potential subgroup identifier	Case records	Frequency analysis and Summary statistics (n, mean, median, standard deviation, minimum and maximum) for dose
Concomitant (non-AD) treatment	Baseline characteristics, outcome, potential confounder, potential subgroup identifier	Case records	Frequency analysis with respect to level 1 and level 2 of ATC codes
Dosage of abrocitinib used	Exposure, potential confounder, explorative outcome variable, potential subgroup identifier	Case records	Summary statistics (n, mean, median, standard deviation, minimum and maximum)
Compliance with abrocitinib treatment (patients' reported compliance)	potential confounder, explorative outcome	Case records	Frequency analysis
Reasons for start of abrocitinib therapy	Explorative outcome variable	Case records	Frequency analysis
Reasons for prescribed dose of abrocitinib therapy	Explorative outcome variable	Case records	Frequency analysis
Reasons for discontinuation of abrocitinib therapy	Explorative outcome variable	Case records	Frequency analysis
Number of flares	Explorative outcome variable	Case records	Summary statistics (n, mean, median, standard deviation, minimum and maximum)
Number of hospitalizations due to AD	Explorative outcome variable	Case records	Summary statistics (n, mean, median, standard deviation, minimum and maximum)
Number of absent days at work/study due to AD Explorative outcome variable		Case records	Summary statistics (n, mean, median, standard deviation, minimum and maximum)

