9.2.3. Study Period

The planned observation period of each patient is 12 months. In this time period up to 6 visits will be documented.

Figure 2. Study Period Start of Month 1 data Month 3 data Month 6 data Month 9 data Month 12 data collection collection collection collection 9 12 0 3 6 1

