9.2.4.5. Treatment of Atopic Dermatitis with Abrocitinib

At the baseline visit (Visit 1) reason of starting or re-starting treatment with abrocitinib will be documented. At each visit (Visit 1-6) dose of treatment with abrocitinib and reason for its choice will be documented. If an escalation or a de-escalation of dosage occurred since the last visit, in addition stop date of previous dosage, start date of new dosage and reason for switch (lack of efficacy or intolerability) will be documented.

If treatment with abrocitinib got terminated since the last visit, reasons for ending abrocitinib treatment, stop date of treatment, start date of other new treatment and reason for switch (lack of efficacy or intolerability) will be documented.

At Visits 2-6, the investigator will ask the patient for his or her self-assessment of compliance in terms of number of abrocitinib-free days since the last visit.

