9.7. Data Analysis

Due to the nature of the study data, descriptive statistics will be used to summarize all endpoints. No formal hypothesis will be tested.

Detailed methodology for summary and statistical analyses of data collected in this study will be documented in the SAP, which will be dated, filed and maintained by the sponsor. The SAP may modify the plans outlined in the protocol; any major modifications of primary endpoint definitions or their analyses would be reflected in a protocol amendment. Appropriate analysis sets will be defined for statistical analysis.

Time to event endpoints will be investigated using Kaplan-Meier methodology. The time to event will be summarized in terms of medians and 95% confidence interval (CIs). Kaplan-Meier plots of the time to event over the study duration will be presented.

Where appropriate, Cox-Proportional Hazards modelling will be used to assess differences between subgroups.

Definition of time windows for study visits

In order to collect comparable study data, Visits 1 to 3 occurring ± 14 days and Visits 3 to 6 occurring ± 28 days of the scheduled visit date will be used for data analysis. However, for analysis of safety parameters, all AEs/SAEs documented within the applicable reporting period will be analyzed.

Visit Label	Target Day	Definition [Day window]
Enrollment	1	1
Month 1	30	16 to 44
Month 3	91	77 to 105
Month 6	182	154 to 210
Month 9	273	245 to 301
Month 12	365	337 to 393

- For the lab values, if the calculated study day for the labelled baseline visit is not study Day 1, but falls within 40 days before the start of the study dosing, then that data should be used for the baseline instead of leaving baseline missing.
- For the other values, if the calculated study day for the labelled baseline visit is not study Day 1, but falls before the start of the study dosing, then that data should be used for the baseline instead of leaving baseline missing.
- If baseline is missing there will be no imputation and although the subject's data will be included in summary data it will not be included in any change from baseline analyses.

If two or more routine visits fall into the same window, keep the one closest to the Target Day. If two routine visits are equal distance from the Target Day in absolute value, the later visit should be used.

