Baricitinib, a JAK1/2 inhibitor, has been approved in 2020 as first small molecule for adult patients with moderate to severe AD who are eligible for systemic therapy. Baricitinib is taken orally as a tablet. According to the applicable summary of product characteristics of baricitinib, laboratory monitoring of lipid parameters, neutrophil count, lymphocyte count, hemoglobin, and liver transaminases should be performed while taking baricitinib. The use of baricitinib is associated with an increased risk of infections such as upper respiratory tract infections [15]

Most recently (in July 2021), upadacitinib a JAK1 inhibitor as second small molecule has been approved by the EMA for the treatment of adults and adolescents (≥12 years) with moderate to severe atopic dermatitis. Like baricitinib, upadacitinib is also taken orally as a tablet. According to the applicable Summary of Product Characteristics (SmPC) monitoring of neutrophil and lymphocyte count, hemoglobin, liver transaminases, and lipid parameters is strictly recommended. Also, upadacitinib use is associated with an increased risk of infections. The most frequent serious infections reported with upadacitinib included pneumonia and cellulitis [16].

However, there is still an unmet medical need for a conveniently administered therapy with an acceptable safety profile, for continuous and intermittent use, which is effective for moderate to severe AD and has a rapid onset of action including for the relief of pruritus.

Abrocitinib: Mechanism of Action (MoA)

Abrocitinib (PF-04965842) is an orally bioavailable small molecule being developed as an oral treatment for patients with moderate to severe AD, therefore it provides a more convenient route of administration compared with the subcutaneous injection required for dupilumab and does not have the potential risk of injection site reactions. Unlike dupilumab, abrocitinib is a small molecule and there is no anticipated immunogenicity to abrocitinib, and so it is unlikely to generate antidrug antibodies and may be used intermittently.

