treated patient will be recorded. In order to understand not only the treatment management and reasons for starting treatment with abrocitinib, but also the reasons for ending therapy with abrocitinib, all patients will be followed up for the full individual observation period of 12 months after first abrocitinib prescription after inclusion in this observational study regardless of whether they are constantly treated with abrocitinib.

Taking into account the more diverse patient population in the real-world setting, this non-interventional study will further provide additional short-and long-term real-world evidence for the effectiveness of abrocitinib in patients of medical interest and need, who may have been underrepresented in the controlled settings of clinical trials and evaluate patient-relevant endpoints including measurements of patient-reported outcomes, such as quality of life, depression, pruritus, and sleep quality.

Patient preference and satisfaction of a therapy strongly affects adherence to a prescribed medication, ultimately affecting treatment outcome and efficacy. A factor known to have an impact on patient satisfaction with a prescribed treatment is the route of administration. Here, several studies point to a preference for oral therapies. Thus, this non-interventional study will document patient's expectations and satisfaction with regards to the treatment.

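### Total days on abrocitinib is a calendar span that counts interruptions as treatment and has no rule for patients still on drug or lost, and no Kaplan-Meier analysis is planned

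*SAP*

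**What the plan says.** SAP 6.3 computes total days of abrocitinib treatment as "Date of last treatment – date of first treatment +1" and reports n, mean, median, SD, minimum and maximum. A second row uses the same span, "stratified by the abrocitinib dose most often applied during the study". SAP 8.2.3 lists both rows for FAS, mFAS and PP, with "Mann-Whitney-U test for subgroups" and missing data marked as excluded. SAP Appendix 1 gives the same formula but words it over AD treatment, not abrocitinib.

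Follow-up is fixed: "The planned observation period of each patient is 12 months" (Protocol 9.2.3). SAP 1 follows patients "regardless of whether they are constantly treated with abrocitinib" and says that abrocitinib "may be used intermittently". Under Protocol 9.2.4.5 a stop date is recorded only if treatment was terminated. At Visits 2 to 6 the investigator also records the patient's "self-assessment of compliance in terms of number of abrocitinib-free days since the last visit". SAP 6.3 uses compliance only as a frequency table.

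Protocol 9.7 states: "Time to event endpoints will be investigated using Kaplan-Meier methodology", with medians and 95% CIs, and Cox modelling of subgroup differences where appropriate. The SAP contains no time-to-event endpoint, no censoring rule and neither method.

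**The concern.** The span can misstate use of abrocitinib in three ways.

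- **Gaps.** Days off drug between the first and last dose are counted as days on drug. The data that would correct this are collected but not used in the formula.
- **Open-ended treatment.** A patient still on drug at month 12, or lost while on drug, has no stop date. The partial-date rule in SAP 7 covers a missing day or month, not an absent date. The analyst must choose between the last known date and exclusion, and the two choices give very different answers.
- **Reading the median.** When more than half the patients are still on drug at month 12, the median span reflects the end of observation or loss, not the time at which patients stop.

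Usage, including dosage and actual use, is among the stated objectives (Protocol 8, SAP 1.3), so a duration figure is likely to be quoted. The subgroup tests carry the same problem. One subgroup in SAP 5.4 compares patients who switched from abrocitinib with those who remain on it. For those who remain, the span to the last known date is simply their length of follow-up.

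**Working it through.** The documents state no expected duration, retention or loss rate, so there is no plan figure to reproduce. The rates below are assumptions.

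**Inputs.** Span formula: SAP 6.3. Administrative end at day 365: the Month 12 target day in Protocol 9.7. Assumed central case: 60% still on drug at 12 months and 20% yearly loss, with constant and independent hazards. Assumed range: 40–80% retention and 0–30% loss.

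**Step 1: gaps.** Overstatement = gap / (span − gap). In a 365-day span:

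| Off-drug days | Days on drug | Overstatement |
|---|---|---|
| 14 | 351 | 4.0% |
| 28 | 337 | 8.3% |
| 60 | 305 | 19.7% |
| 90 | 275 | 32.7% |

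**Step 2: ongoing and lost patients, central case.** Stopping hazard λ = −ln(0.60)/365 = 0.0013995 per day. Loss hazard μ = −ln(0.80)/365 = 0.0006114. Sum s = 0.0020109.

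- True mean within 12 months: (1 − 0.60)/λ = 0.40/0.0013995 = 286 days. Kaplan-Meier recovers this restricted mean. Its median is not reached, because 60% are still on drug at day 365.
- Last known date taken as the end: mean (1 − 0.60 × 0.80)/s = 0.52/0.0020109 = 259 days. Median ln 2/s = 344.7 days (344 in simulation).
- Patients without a stop date excluded: the share with a stop date is (λ/s) × 0.52 = 0.696 × 0.52 = 0.36, so 64% are omitted. Mean 1/s − 365 × 0.48/0.52 = 497.3 − 336.9 = 160 days (161 in simulation).

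The two undefined readings therefore differ by about 100 days (259 against 161).

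**Step 3: range.** Simulation with 300,000 patients per scenario, retention 40–80%, last known date taken as the end:

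| 12-month loss | Span mean below the true 12-month mean by |
|---|---|
| 0% | 0 days (means 239 to 327, equal to the truth) |
| 10% | 10–16 days |
| 20% | 21–32 days |
| 30% | 32–50 days |

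With no loss and retention of 60% or more, the span median shows 365 where the Kaplan-Meier median is not reached. Under exclusion, the mean stays at 145–176 days whatever the true retention, with 40–83% of patients omitted.

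**Step 4: can free days simply be subtracted?** Not as collected. They are counted since the last visit, so they can include days after the stop. Take a patient who stops on day 60 and is seen on day 91. About 31 post-stop days would be taken from a 60-day span, leaving 29. Only free days between first and last dose may be subtracted.

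**The case against.** The strongest reply is that this row is an exposure summary labelled total days and not a persistence endpoint. Within a fixed 12-month window, the mean span of patients followed to month 12 is a legitimate quantity, and Step 3 confirms no bias with zero loss, gaps apart. Protocol 9.9 expects follow-up beyond discontinuation to keep more patients in the study. Compliance is tabulated separately, the subgroup tests are explicitly explorative, and no decision rule depends on them. All of that stands and limits the point.

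A reader might infer more than the documents support:

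- That the SAP treats ongoing patients as having stopped. It does not say so; the date is undefined, and exclusion is equally open.
- That persistence is a stated objective. The objectives name usage, dosage and actual use, and reasons for ending treatment.
- That omitting Kaplan-Meier breaches the protocol. Protocol 9.7 ties the method to no named endpoint and lets the SAP modify its plans.
- That the true median stopping time (about 495 days at 60% retention) is the yardstick. It lies beyond the observation window, so the 12-month restricted mean is the fair comparison.

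The reply does not remove the formula's treatment of gaps, the missing rule for open-ended treatment, or the unexplained absence of any time-to-event analysis.

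**Conclusion.** The point holds in a limited form. That gaps count as treatment follows directly from the formula; the size depends on how long interruptions last (8.3% for an assumed 28 days in a 365-day span). The error for ongoing and lost patients depends on an unstated choice. In the assumed central case the mean is about 27 days too low (259 against 286) if last contact is used, and about 125 too low (161 against 286) if patients without a stop date are dropped. These figures rest on constant hazards and on loss unrelated to stopping. With complete 12-month follow-up and the month-12 date used, only the gaps and the reading of the median as time to stopping remain. The variable is exploratory, so primary and secondary endpoints are unaffected. The change is worth making before database lock, so that the choice between readings is not made after seeing the data.

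**What to change.** Amend SAP 6.3, 8.2.3 and Appendix 1 as follows.

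- **(a) Anchor the span.** Start at the first abrocitinib dose after inclusion and restrict it to abrocitinib, replacing the AD-treatment wording. Re-initiators are eligible (Protocol 9.2.1), so an unanchored first date could precede inclusion, and AD treatment could take in later drugs.
- **(b) Add time to abrocitinib discontinuation.** Pre-set an analysis rule for gaps and restarts. Censor ongoing or lost patients at the last documented on-treatment date. Report Kaplan-Meier estimates at 3, 6 and 12 months with 95% CI, and use this analysis, not Mann-Whitney tests on raw spans, to compare duration between subgroups.
- **(c) Report days on drug separately.** Use the span minus only those abrocitinib-free days that fall between first and last dose, and give the number of patients whose free-day reports are incomplete.

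The cost is SAP wording, a gap definition, and one extra table and figure. Stop dates and free days are already collected. Two weaknesses remain: free days are self-reported, and no visit is mandatory, so some reports will be missing. Placing free days before or after a stop between visits may also need a stated convention.
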